- **Partial-onset seizures**

Is TROBALT indicated for use as monotherapy?

- **No**

What is the maximum recommended daily maintenance dose of TROBALT for most patients?

- **1200 mg**

Which one of the following statements is true? (Please select the best response.)

- TROBALT should be taken once a day.
- TROBALT should be taken twice a day.
- **TROBALT should be taken three times a day. [CORRECT RESPONSE]**
- TROBALT should be taken four times a day.

When increasing the dose, what is the maximum total daily dose at which TROBALT can be increased once every 7 days?

- **150 mg**

Which one of the following statements is true?

- There are no lower age limits for TROBALT usage.
- The youngest age at which TROBALT can be used is 12.
- **The youngest age at which TROBALT can be used is 18. [CORRECT RESPONSE]**

The quickest time by which the minimum maintenance dose of 600mg should be reached is the third week?

- **True**

For the general population, the recommended total initial dosage should be 150mg per day for one week.

- **False**
The starting dose is 300 mg/day

People taking TROBALT had a higher chance of experiencing which of the following risks in clinical studies?

- Urinary retention
- Confusional state
- Hallucinations
- Psychotic disorders

It is known from controlled studies that adverse events related to voiding dysfunction generally tend to be reported how soon after starting TROBALT?

- **Within the first 8 weeks**

It is known from controlled studies that confusional state, hallucinations, and/or psychotic disorders generally tend to be reported how soon after starting TROBALT?

- **8 weeks**

Which of the following urinary symptoms, if any, should you specifically advise patients taking TROBALT to watch out for?

- Pain when urinating
- Difficulty starting urination
- Slow stream
- Inability to pass urine
- **All of the above**

According to the TROBALT Physician's Guide, appropriate dose titration may minimize the risk of which of the following adverse events?

- **CNS side effects such as hallucinations**

[DO NOT DISPLAY THE FOLLOWING TWO QUESTIONS FOR RESPONDENTS FROM SWITZERLAND]

Using the Treatment Initiation Pack, by which week can the patient reach a dose of 600mg/day?

- **3 weeks**

At what dose has TROBALT been shown to produce a possible QT prolonging effect?

- **1200mg**

For which patient is it recommended that an ECG is recorded before initiating TROBALT?

- Patients with congestive heart failure
- Patients with ventricular hypertrophy
- Patients with hypokalemia

What should you do in a patient with a QTc of less than 440ms before starting TROBALT?

- **Recheck the ECG after reaching the maintenance dose**

Which new cardiac effects in particular should you warn your patients about after prescribing TROBALT?

- Syncope
- Palpitations
- Any other symptoms of arrhythmia
- **All of above**

Please refer to the Physician's Guide and the TROBALT Prescribing Information for further details.

THANK YOU

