To ensure comprehension of each communication piece, all of the physician and patient outreach will be conducted in the local country language. Specifically, the surveys and invitation letters will all be translated by a certified translation company. In addition, when conducting the survey by telephone, the person conducting the survey will be a native language speaker.

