3.3.2. Measures to minimise bias in the surveys

The following are measures to minimise bias in the surveys:

- Telephone interviewers are highly trained and use a standardized script to administer interviews.
- All questions will be programmed to ensure that questions are asked in the appropriate sequence. Skip patterns will be clearly indicated. Respondents cannot go back to a question once the question has been answered and cannot skip ahead. All questions must be answered in order to complete the survey.
- Response options presented in a list will be randomized to minimize positional bias.
- Programming will be reviewed by quality control and simulated users (User Acceptance Testing) prior to implementing the survey.

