4.4. Neurologist Outcomes

Neurologist understanding of the significant risks associated with TROBALT will be assessed using a standardised questionnaire.

The primary outcome of this study is the proportion of neurologists that correctly respond to individual survey questions concerning the risks associated with TROBALT. The proportion responding correctly will be tabulated separately for each item in the physician understanding survey instrument. These risks represent those described in the Physician's Guide for TROBALT.

Physician demographic information will be collected at the end of the survey in order to further characterise the respondent population. This will include gender and medical specialty, type of medical practice, years in medical practice. Country in which practice occurs will be collected at the beginning of the survey in order to identify respondents from Switzerland for whom not all questions apply.

At the conclusion of the online survey, the final screen will display a summary of the relevant information from the Physician's Guide.

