6.2.2. Neurologist survey analysis

The primary outcome is the proportion of neurologists answering each question of the understanding of the risks associated with TROBALT correctly. Point estimates for the proportion with correct responses, and associated confidence intervals, will be calculated for each question about the risks of TROBALT. In the case of multiple choice questions, the number and proportion of neurologists reporting each response will also be provided.

The proportion of correct answers to survey questions will be summarised overall, and separately for those neurologists who have prescribed TROBALT. Exploratory analyses may include stratification by country.

The survey results will be presented with Germany included in the overall study population, then separately for Germany and the remaining specified European countries.

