10. APPENDICES

Appendix 1 Template for the letter to prescribers including the TROBALT Physician's Guide

Physician address
Date

Dear Physician (or personalise with Dr and surname where possible)

Introducing new Trobalt (retigabine): a first-in-class potassium channel opener for the adjunctive treatment of epilepsy¹

GlaxoSmithKline is pleased to announce the recent marketing authorisation of Trobalt in (country). Trobalt is licensed for partial onset seizures with or without secondary generalisation in adults aged 18 years and above with epilepsy.¹

The approval was supported by the results of the pivotal phase III studies RESTORE 1 and 2, which showed that significantly more patients with uncontrolled epilepsy saw a reduction of 50% or more in seizure frequency compared to placebo when a 600mg/day, 900mg/day or 1200mg/day dose of Trobalt was added to their current anti-epileptic drug (AED) regimen.^{2,3}

Trobalt is a first-in-class AED that is thought to primarily target potassium channels in the brain⁴ which play a major role in seizures and in regulating neuronal function, providing a new therapeutic option for the treatment of uncontrolled epilepsy.^{5,6}

To date, 45 studies investigating Trobalt (phase I, II and III) have been completed evaluating more than 2,000 subjects, including 1,365 patients with epilepsy.⁷

Trobalt has been shown to be generally tolerated with most reported adverse events being transitory, mild to moderate in severity and occurring early during the titration period. Very common side effects were dose-related and included dizziness, somnolence and fatigue¹

AEDs may have specific considerations to ensure appropriate prescribing. With Trobalt, the following advice should be discussed with your patients before initiating therapy.

Trobalt must be taken orally, with or without food, in three divided daily doses. Tablets should be swallowed whole and not chewed, crushed or divided. Trobalt must be titrated to reach an effective dose. The starting dose is 300 mg/day, increased by 150 mg/day weekly according to patient response and tolerability. The maximum total daily dose is 1200 mg/day.¹

Treatment initiation packs are available for patients using the standard dose titration regimen to facilitate the first 2 weeks of therapy, and reach a potentially therapeutic dose of 600 mg/day by the third week of therapy.

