The information in this survey and the Patient Information Leaflet (PIL) should not take the place of talking with your health care professional. If you have any questions about your condition or treatment, or if you would like more information about TROBALT, talk to your health care professional. The Patient Information Leaflet can be obtained from the following website: <http://www.gsk.com/products/prescription-medicines/trobalt.htm>.

Thank You

Appendix 5 Questionnaire for Neurologists who Prescribe AEDs and were Sent the TROBALT Letter Containing the Physician's GuideScreening Questions:

1. Do you agree to take part in this survey?
 - **Yes**
 - No (Exclude)

2. When was the last time you prescribed an anti-epileptic drug for a patient?
 - **Less than a month ago**
 - Between 1 and 2 months ago
 - Between 2 and 3 months ago
 - More than 3 months ago (Exclude)

3. Have you ever prescribed TROBALT?
 - **Yes**
 - No
 - I don't know

4. In which country is your primary medical practice?
 - **Germany**
 - Denmark
 - United Kingdom
 - Switzerland
 - Sweden
 - Spain
 - Slovakia
 - Norway
 - Other (exclude)

[QUOTAS WILL BE ESTABLISHED FOR 200 NEUROLOGISTS FROM UK, SWEDEN, DENMARK, SWITZERLAND, SPAIN, SLOVAKIA, AND NORWAY; AT LEAST 75 SHOULD HAVE PRESCRIBED TORBALT. QUOTA OF 100 NEUROLOGISTS FROM GERMANY, OF WHICH AT LEAST 50 SHOULD HAVE PRESCRIBED TROBALT.]

5. Are you an employee of GlaxoSmithKline or [REDACTED] Corporation?
 - **Yes (Exclude)**
 - **No**

Questionnaire for Neurologists who Prescribe AEDs and Were Sent the TROBALT Letter Containing the Physician's Guide

[CORRECT ANSWERS ARE INDICATED IN BOLD]

6. For which of the following conditions is TROBALT approved for use?
- Migraine
 - **Partial-onset seizures**
 - All types of seizures
 - All of the above
 - None of the above
 - I don't know
7. Is TROBALT indicated for use as monotherapy?
- Yes
 - **No**
 - I don't know
8. What is the maximum recommended daily maintenance dose of TROBALT for most patients? (Please select the best response.)
- 600 mg
 - 900 mg
 - **1200 mg**
 - 2000 mg
 - None of the above
 - I don't know
9. Which one of the following statements is true? (Please select the best response.)
- TROBALT should be taken once a day.
 - TROBALT should be taken twice a day.
 - **TROBALT should be taken three times a day.**
 - TROBALT should be taken four times a day.
 - None of the above
 - I don't know

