10. When increasing the dose, what is the maximum total daily dose at which TROBALT can be increased once every 7 days? (Please select the best response.)
- 50 mg
 - **150 mg**
 - 300 mg
 - 600 mg
 - None of the above
11. Which one of the following statements is true? (Please select the best response.)
- There are no lower age limits for TROBALT usage.
 - The youngest age at which TROBALT can be used is 12.
 - **The youngest age at which TROBALT can be used is 18.**
 - I don't know

Please respond “true,” “false” or “I don’t know” to each of the following questions:

12. The quickest time by which the minimum maintenance dose of 600mg should be reached is the third week?
- **True**
 - False
 - I don’t know
13. For the general population, the recommended total initial dosage should be 150mg per day for one week.
- True
 - **False**
 - I don’t know
14. People taking TROBALT had a higher chance of experiencing which of the following risks in clinical studies? (Please select all that apply)
- **Urinary retention**
 - **Confusional state**
 - **Hallucinations**
 - **Psychotic disorders**
 - Myocardial infarction
 - Renal carcinoma
 - All of the above
 - None of the above
 - I don’t know
15. It is known from controlled studies that adverse events related to voiding dysfunction generally tend to be reported how soon after starting TROBALT?
- Within the first week
 - **Within the first 8 weeks**
 - After 4 months
 - After 12 months
 - I don’t know
16. It is known from controlled studies that confusional state, hallucinations, and/or psychotic disorders generally tend to be reported how soon after starting TROBALT?
- 4 weeks
 - **8 weeks**
 - 12 weeks
 - 16 weeks
 - I don’t know

17. Which of the following urinary symptoms, if any, should you specifically advise patients taking TROBALT to watch out for? (Please select the best response.)
- Pain when urinating
 - Difficulty starting urination
 - Slow stream
 - Inability to pass urine
 - **All of the above**
 - None of the above
 - I don't know
18. According to the TROBALT Physician's Guide, appropriate dose titration may minimize the risk of which of the following adverse events? (Please select the best response.)
- QT prolongation
 - **CNS side effects such as hallucinations**
 - Urinary retention
 - All of the above
 - None of the above
 - I don't know

[DO NOT DISPLAY QUESTIONS 19 and 20 FOR RESPONDENTS FROM SWITZERLAND]

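### Neurologist Question 10 asks for a maximum total daily dose but keys the 150 mg weekly increase, so a knowledgeable literal reader can be scored wrong

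*Protocol*

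**What the plan says.** Appendix 5, Question 10 reads "When increasing the dose, what is the maximum total daily dose at which TROBALT can be increased once every 7 days". The options are 50, 150, 300 and 600 mg and *None of the above*. The questionnaire states "CORRECT ANSWERS ARE INDICATED IN BOLD", and 150 mg is in bold. The closing text of Appendix 5 repeats the stem and gives 150 mg again.

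The survey tests the letter in Appendix 1, which describes the titration in two consecutive sentences: "The starting dose is 300 mg/day, increased by 150 mg/day weekly according to patient response and tolerability", then "The maximum total daily dose is 1200 mg/day".

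Section 4.4 defines the endpoint: "The primary outcome of this study is the proportion of neurologists that correctly respond to individual survey questions". Section 6.2.2 adds, for multiple choice questions, that "the number and proportion of neurologists reporting each response will also be provided". Section 3.3.2 states "All questions must be answered in order to complete the survey" and does not let respondents return to an answered question. Under Section 3.1, "the surveys and invitation letters will all be translated by a certified translation company".

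**The concern.** The stem uses the letter's own term for the 1200 mg/day ceiling, while the key is the letter's figure for the weekly step. A respondent who reads the stem in the letter's terms looks for 1200 mg, finds that the options stop at 600 mg, and is left with *None of the above*. That answer counts as incorrect even if the respondent knows the step is 150 mg/day.

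The item must be answered and, unlike Questions 8 and 9, offers no *I don't know*. A neurologist who does not know the step may therefore choose *None of the above* too. The planned response distribution would show a build-up on that option but could not separate the two groups.

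Question 10 is the only item that asks directly for the size of the titration step. The letter links appropriate titration to a lower risk of central nervous system effects, and the protocol intends the results to guide revision of the key messages. A low score caused by the wording could be read as a message that failed.

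**Working it through.** **1. Is 150 mg ever a total daily dose?** Inputs from Appendix 1: start at 300 mg/day, add 150 mg/day each week, stop at 1200 mg/day.

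Dose in week w = min(300 + 150 × (w − 1), 1200) mg/day.

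| Week | 1 | 2 | 3 | 4 | 5 | 6 | 7 |
|---|---|---|---|---|---|---|---|
| mg/day | 300 | 450 | 600 | 750 | 900 | 1050 | 1200 |

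Week 3 gives 600 mg/day, which reproduces the letter's own milestone. So 150 mg is the increment and never a total daily dose in this schedule. It lies below the starting dose, and Question 13 treats 150 mg per day as a false initial dose.

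**2. What does a literal reader answer?** Read in the letter's terms, the answer is 1200 mg/day. If the stem is read as the last dose from which a full step still fits, it is 1050 mg/day. Neither is offered, so both readings lead to *None of the above*.

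**3. How large could the loss be?** Let k be the share who know the step and m the share of those who read the stem literally. Then, ignoring lucky guesses, observed proportion correct = k × (1 − m), and loss = k × m. The protocol gives neither k nor m; both are assumed here.

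With k = 80%:

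| m | Loss (points) | Observed |
|---|---|---|
| 5% | 0.80 × 5 = 4 | 76% |
| 10% | 0.80 × 10 = 8 | 72% |
| 20% | 0.80 × 20 = 16 | 64% |

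**4. Comparison with sampling error.** The loss equals the margin of error when m = margin / k. Margins are from Table 1 in Section 7:

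| n | k | Table 1 margin | Break-even m |
|---|---|---|---|
| 200 | 60% | 7.0 | 7.0 / 60 = 11.7% |
| 200 | 80% | 5.5 | 5.5 / 80 = 6.9% |
| 200 | 90% | 4.0 | 4.0 / 90 = 4.4% |
| 300 | 80% | 4.7 | 4.7 / 80 = 5.9% |

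As a check, 1.96 × √(0.8 × 0.2 / n) gives 5.5 points at n = 200 and 4.5 at n = 300. The second is slightly below the Table 1 entry and would put the break-even at 5.7%, an immaterial difference.

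**5. Extent.** Questions 6 to 23 are the knowledge items: 23 − 6 + 1 = 18. Only Question 10 has this fault.

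**The case against.** The strongest reply is that few neurologists would be caught. The stem opens by referring to dose increases and ends with a weekly interval. Question 8 has already asked for the 1200 mg maximum. Question 10 does not offer 1200 mg, it lists two figures below the starting dose, and it asks for the best response. A neurologist who knows the step and sees 150 mg listed will often choose it. This stands: many readers will recover the intent, and nothing in the protocol shows how many will not.

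The clash of terms is also visible only in English. Most respondents will see translations, which could remove it or carry it over. This stands as uncertainty about size, and it is a reason to correct the English source first.

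Guessing works in the other direction. If the 20% who do not know the step guessed evenly among five options, 0.20 × 0.20 = 4 points would be added, cancelling the 5% scenario. The arithmetic is right, and the net bias at low misreading rates is therefore uncertain. But guessing is a separate error, linked to the missing *I don't know* option. If guessing is the same under either wording, the current stem still scores k × m points below a correct one. Two errors that may partly cancel are no reason to keep either.

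The missing *I don't know* is not peculiar to this item: Questions 19 and 23 lack it as well. It is a secondary point here.

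Finally, the study is descriptive, the protocol states no pass mark or composite score for neurologists, and Questions 12, 13 and 19 cover neighbouring titration facts. That limits the consequence. It does not make the Question 10 estimate valid, and the protocol plans no cross-check between these items.

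**Conclusion.** The concern holds. The stem of Question 10 does not ask for the quantity that its key gives, and it borrows the letter's term for a different quantity. The key itself is right for the evident intent.

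Literal reading can only lower the proportion correct, and a larger sample does not reduce that loss. Its size is unknown. On the assumption of 80% true knowledge, it matches the Table 1 margin when 6.9% (n = 200) or 5.9% (n = 300) of those who know the step read the stem literally; below those rates it is smaller than sampling error. The damage is confined to the estimates for one of 18 items. This should be corrected, but it does not threaten the survey as a whole.

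**What to change.** In Appendix 5, change the stem of Question 10 to ask for the increment, for example: *By how much, at most, may the total daily dose of TROBALT be raised every 7 days?* Give the options in mg/day, keep 150 mg/day as the key, and add *I don't know* as in Questions 8 and 9. Make the same change to the stem in the closing text, which otherwise shows respondents the wrong description of 150 mg.

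Make the change in the English source before the questionnaire goes to the translators. The cost is an edit to one stem, its options and its closing text, with no added respondents, procedures or analyses.

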- 1) 250 patients recruited from across the following countries (United Kingdom, Sweden, Denmark, Switzerland, Spain, Slovakia and Norway) and up to 100 patients from Germany who are currently using or have filled a prescription for TROBALT at least once in the last 3 months.
- 2) 200 neurologists who have prescribed an anti-epileptic drug (AED) at least once in the last 3 months, and who were on the list to which a letter containing the Physician's Guide for TROBALT was distributed from across the following countries (United Kingdom, Sweden, Denmark, Switzerland, Spain, Slovakia and Norway). At least 75 of the neurologists will have prescribed TROBALT. The survey will also aim to include up to 100 neurologists from Germany of which approximately 50 will have prescribed TROBALT.

Patients eligible for the survey will be asked to take the survey online or via a telephone interview if the latter is preferred. Neurologists will be invited to take the survey online.

The selected countries were the first five countries to launch TROBALT (Germany, Denmark, United Kingdom, Switzerland and Sweden) and an additional three countries with launch in 2011, but with relatively high rates of uptake of TROBALT (Spain, Slovakia and Norway). The selection of countries includes Switzerland, which is not part of the European Union. However, the key messages regarding the risks with TROBALT are in alignment. The rationale for surveying the first five countries to launch is so that any issues identified from these countries regarding the effectiveness of the Physician's Guide and PIL in communicating the risks of TROBALT can be addressed as soon as possible, and the key messages can be revised in a timely manner. In addition, these countries are likely to provide the greatest number of neurologists with experience of prescribing TROBALT, and their patients.

Study Endpoints/Assessments

The primary outcome of the survey is the proportion of patients/neurologists providing correct responses to a series of questions concerning the significant risks associated with TROBALT. The risks evaluated will be those described in the TROBALT PIL and in the Physician's Guide.

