Appropriate dose titration may minimise the risk of central nervous system-related adverse events, including hallucination and psychotic disorders.

Date of preparation: May 2011
NECE/RTG/0033/11

Prescribing Information is available on the back page

Trobalt™
retigabine tablets

1. Urinary effects

Urinary retention, dysuria and urinary hesitation were reported in controlled clinical studies with Trobalt, generally within the first 8 weeks of treatment. Trobalt must be used with caution in patients at risk of urinary retention, and it is recommended that patients are advised about the risk of these possible effects.¹

Does your patient have symptoms of urinary retention e.g. hesitancy, poor stream?

Does your patient take drugs that can cause urinary retention e.g. anticholinergics?

Is your patient able to communicate new symptoms of urinary retention?

2. QT interval prolongation

A study of cardiac conduction in healthy subjects has demonstrated that Trobalt titrated to 1200 mg/day produced a QT prolonging effect. A mean increase in Individual Corrected QT Interval (QTcI) of up to 6.7 ms (upper bound of 95% one-sided CI 12.6 ms) was observed within 3 hours of dosing.¹

Caution should be taken when Trobalt is prescribed with medicinal products known to increase QT interval and in patients with known prolonged QT interval, congestive cardiac failure, ventricular hypertrophy, hypokalaemia or hypomagnesaemia and in patients initiating treatment who are 65 years of age and above.¹

In these patients it is recommended that an electrocardiogram (ECG) is recorded before initiation of treatment with Trobalt and in those with a corrected QT interval >440 ms at baseline, an ECG should be recorded on reaching the maintenance dose.¹

Does your patient have a history of cardiac disease?

Does your patient take drugs that are known to cause QT prolongation?

Retigabine has not been shown to cause cardiac arrhythmias in the randomised clinical trials, however patients should be advised to report new symptoms that might indicate a prolonged QT interval, for example palpitations, syncope.

3. Psychiatric effects

During controlled clinical studies, confusional state, psychotic disorders and hallucinations were reported, generally within the first 8 weeks of treatment. It is recommended that patients are

Date of preparation: May 2011
NECE/RTG/0033/11

Trobalt™
retigabine tablets

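### Neurologist Question 15 has overlapping options and a gap after 8 weeks, so it mainly separates early from late onset and probably overstates knowledge of the 8-week urinary message

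*Protocol*

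**What the plan says.** The Guide letter in Appendix 1 gives the urinary message: "Urinary retention, dysuria and urinary hesitation were reported in controlled clinical studies with Trobalt, generally within the first 8 weeks of treatment". It describes the timing of psychiatric effects in the same 8-week terms.

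Appendix 5 tests the urinary message in Question 15: "It is known from controlled studies that adverse events related to voiding dysfunction generally tend to be reported how soon after starting TROBALT". The substantive options are "Within the first week", "Within the first 8 weeks" (the key), "After 4 months" and "After 12 months", and there is a don't-know option. The closing answer screen repeats the same key.

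Question 16 tests the psychiatric message: "It is known from controlled studies that confusional state, hallucinations, and/or psychotic disorders generally tend to be reported how soon after starting TROBALT". Its options are bare time points of 4, 8 (key), 12 and 16 weeks, plus don't know.

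Under Sections 4.4 and 6.2.2, the proportion of neurologists answering each individual question correctly is the primary outcome, reported item by item with a confidence interval. Section 6.2.2 adds the count and proportion giving each response for multiple-choice questions. Section 3.3.1 rules out open-ended questions. Section 3.3.2 requires every question to be answered, forbids going back, and randomises the order of listed options.

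**The concern.** A multiple-choice item measures a specific message only if someone who does not hold that message has a wrong option to choose. For the 8-week statement, the wrong beliefs most easily confused with it are nearby windows such as 4, 6 or 12 weeks. Question 15 has no option for any of these. A respondent with only a general sense that urinary effects come early is steered to the key and scored as knowing the 8-week window.

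Each item stands alone as a primary outcome, so a weak item is not diluted in a summary score. A high figure for Question 15 could be reported as evidence that the Guide conveyed the timing of urinary effects, when it may show only that neurologists expect them early. Because the believed window is not recorded, analysis cannot repair this afterwards, and a larger sample does not reduce it.

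**Working it through.** The plan states no figure that depends on Question 15, so the main check is logical. An assumed calculation follows, for scale only.

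**Options on a time line** (weeks since starting; 4 months = 4 × 365.25 / 12 / 7 = 17.4 weeks)

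| Option | Interval | Relation to the others |
|---|---|---|
| First week | 0 to 1 | inside the key |
| First 8 weeks (key) | 0 to 8 | contains the first-week option |
| none | 8 to 17.4 | uncovered, 17.4 − 8 = 9.4 weeks |
| After 4 months | above 17.4 | contains the after-12-months option |
| After 12 months | above 52 | inside the after-4-months option |

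**Where each belief can go**

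- Window ends at 2, 4 or 6 weeks: the key is the only substantive option that fits. The same holds for any end point above 1 week and up to 8 weeks, which is 7/8 = 87.5% of the 0 to 8 week span.
- Window ends at 10, 12 or 16 weeks: no option matches. Because an answer is compulsory, the respondent takes the nearest option or don't know. The key is the nearest early option.
- First week: this belief has its own option, scored wrong, although it is logically compatible with the key. The stem's phrase about how soon can also be read as asking for earliest onset. Several other items (Questions 8 to 11, 17, 18 and 22) tell the respondent to choose the best response. Question 15, where options overlap, does not.

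**Illustration of size.** Let k be the share who know the 8-week window, e the share of the rest who believe only that effects come early, and c the chance that such a person ticks the key. All three are assumptions. Then

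share scored correct = k + (1 − k) × e × c, and overstatement = (1 − k) × e × c.

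- k = 50%, e = 50%, c = 0.5: 0.5 + 0.5 × 0.5 × 0.5 = 62.5%.
- k = 50%, e = 50%, c = 1: 0.5 + 0.5 × 0.5 × 1 = 75%.
- Smallest overstatement over k = 30% to 70%, e = 30% to 80%, c = 0.5 to 1: 0.3 × 0.3 × 0.5 = 4.5 points.
- Largest over the same ranges: 0.7 × 0.8 × 1 = 56 points.

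**Opposite effect.** If a share d of those who know the window tick the first-week option, the score falls by k × d. With k = 50%, e = 50% and c = 0.5, the 12.5-point overstatement is cancelled when d = 0.125 / 0.5 = 25%.

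**Sampling error for comparison.** The 95% half-width is 1.96 × √(p(1 − p)/n). At p = 50% it is 5.7 points for n = 300 and 6.9 for n = 200. Table 1 gives 5.7 and 7.0.

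**The case against.** The strongest reply is that nothing here is an error. The key matches the letter and the closing screen. The objective in Section 2 is understanding of significant risks, not recall of an exact cut-off, and a neurologist who expects urinary effects within 4 or 6 weeks holds a view compatible with the letter. On that reading, easy distractors are a matter of item-writing taste. Nesting also costs credit when a respondent chooses the first week. Finally, the full response distribution will be reported.

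Much of this stands. The fault is weak discrimination, not a wrong key, and the upward direction is probable rather than certain. The response distribution helps only in part. It will show first-week, late and don't-know choices, but it cannot separate those who know the 8-week window from those who chose the key because it was the only early option left.

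A reader might go further and infer that Question 15 must outscore Question 16 by some definite margin. The documents do not support that. If beliefs are assumed to sit at 4, 8 and 12 weeks, the minimum gap is simply the assumed share at 4 weeks, so it is an input. With k = e = 50% and vague early beliefs split evenly between 4 and 8 weeks on Question 16, that item scores 0.5 + 0.5 × 0.5 × 0.5 = 62.5%, against 62.5% to 75% for Question 15. The gap is then 0 to 12.5 points.

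A reader might also infer that the survey will compare the two items to decide what to revise. No comparison between items is planned. The remark that "the key messages can be revised in a timely manner" explains why the first countries to launch were selected; it is not an item-level decision rule.

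**Conclusion.** The point holds as a minor weakness of one neurologist item. The overlap at both ends and the uncovered stretch of about 9.4 weeks are visible in Appendix 5 and need no assumption. It follows that Question 15 separates early from late onset but hardly tests the 8-week message, and that its proportion correct probably overstates knowledge of that message.

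The size is not derivable from the documents. The 4.5 to 56 point range rests wholly on assumed values of k, e and c. It shows only that the overstatement could be smaller or larger than the sampling error in Table 1. The conclusion also takes the 8-week statement to be what the item is meant to test, which its key and the letter suggest. If the aim were only to check that neurologists expect early onset, the item would largely serve, but the result should then be described in those terms.

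**What to change.** Before launch, replace the Question 15 options with a gap-free list that allows only one defensible answer. For example, ask for the end of the period within which these events were generally reported, and instruct the respondent to select the one period stated in the Physician's Guide. The options would be first 4 weeks, first 8 weeks (key), first 12 weeks, first 16 weeks, no such early period or later than 16 weeks, and don't know.

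The instruction is essential. Without it, the periods are themselves nested and the wider ones are literally true. Question 18 already refers to the Guide in its stem, so the form is not new to the questionnaire.

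Preferably use the same wording for Question 16, which tests the same 8-week statement with bare time points. Align the closing answer screen with both items.

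The cost is two option lists to reword, programme and translate; sample size and analysis are unchanged. The reported proportion correct for Question 15 may be lower. If the list cannot be changed, describe the result as recognition of early onset and show the full response distribution beside it.
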